### 3. STUDY DESIGN

**Type of Study:** Open label, randomised cross-over study at a single centre.

**Number of Subjects:** 12 children will be recruited from the Adolescent Allergy Service at St Mary's Hospital, Paddington.

**Expected Duration:** Recruitment to commence 1st September 2017

Two clinical visits (full day) one month apart, with a follow-up questionnaire one month after the second visit.

Expected completion: 31 July 2018.

### 3.1 STUDY OUTCOMES MEASURES

#### 3.1.1 PRIMARY STUDY OUTCOME

- Plasma catecholamine profile – determined through  $C_{max}$ ,  $T_{max}$ , AUC – following self-injection of adrenaline (300mcg, 500mcg) on separate occasions.

#### 3.1.2. SECONDARY STUDY OUTCOMES

1. Cardiovascular parameters [HR, BP, SV] following self-injection of adrenaline (300mcg, 500mcg) on separate occasions.
2. Plasma catecholamine levels [ $C_{max}$ ,  $T_{max}$ , AUC] and cardiovascular parameters [HR, BP, SV] following self-injection of 300mcg adrenaline using 2 devices with different needle lengths (15mm, EpiPen 0.3mg; 23mm, Emerade 300mcg).
3. Adverse events following AAI administration.
4. Change in HRQL measures (FAQLQ, FAIM, self-efficacy) 1 month following each study visit.

## 4. STUDY POPULATION

This is an open label, randomised-block crossover study to assess the pharmacokinetics/pharmacodynamics of 2 different doses of adrenaline following self-injection with an auto-injector. Laboratory and cardiovascular assessments will be analysed by personnel blinded as to the intervention received.

### 4.1 RECRUITMENT

Subjects will be recruited from the Adolescent Allergy Service at St Mary's Hospital, Paddington. Potential participants will receive the study information leaflets either in person (during a routine clinic appointment) or via email. Interested participants may be screened by telephone to determine suitability for this study.

### 4.2 ELIGIBILITY CRITERIA:

#### 4.2.1 INCLUSION CRITERIA

1. Age 13 – 18 years inclusive
2. Body mass >40kg
3. Prescription of AAI due to physician diagnosis of IgE-mediated food allergy.
4. Written informed consent from parent/guardian together with patient assent, for participants under 16 years of age. For young people age 16+ years, consent will be obtained from the participant themselves.

#### 4.2.2 EXCLUSION CRITERIA

1. Known cardiac comorbidity (including hypertension, structural or electrophysiological diagnoses) or prescribed a medicine to control cardiovascular disease/hypertension.
2. Known endocrine or renal disease
3. Poorly controlled asthma requiring daily rescue treatment with a bronchodilator.
4. Pregnancy
5. Unwilling or unable to comply with study requirements

All participants must be well on the study day, with:

- No fever ( $\geq 38.0^{\circ}\text{C}$ ) in the preceding 48 hours
- No additional  $\beta$ -agonist containing medication (e.g. Salbutamol) or antihypertensive (e.g.  $\beta$ -blocker) in the 72 hours prior to study visit
- No intramuscular adrenaline given in the preceding week

### 4.3 SUBJECT WITHDRAWAL

Parents/guardians may withdraw their child at any time without giving a reason. In accordance with the current revision of the Declaration of Helsinki and any other applicable regulations, the parents or legal representatives of the child have the right to withdraw the participant from the study at any time and for any reason, without prejudice to his or her future medical care, and are not obliged to give his or her reasons for doing so.

The investigator may withdraw a participant from the study at any time if, in the investigator's clinical judgment, it is in the best interests of the participant's health and well-being. In addition the participant may be withdrawn for any of the following reasons:

- Decision by the Investigator
- Ineligibility (either newly arising during the study, or retrospective having been overlooked at screening)
- Significant protocol deviation where this will impact irreversibly on data integrity  
e.g. failure to administer adrenaline autoinjector correctly
- Participant non-compliance with study requirements
- An adverse event which requires discontinuation of the study treatment, or results in inability to continue to comply with study procedures.

If the participant is withdrawn due to an adverse event, the Investigator will arrange for appropriate follow-up through telephone calls (and/or visits if necessary) until the adverse event has resolved or stabilised.

Any data generated from monitoring or samples already taken from a withdrawn participant will be included in the data analyses, unless specific instruction for their destruction is received from the participant or their parent/guardian. Withdrawn participants will be replaced, where feasible.

## 5. STUDY TREATMENT

### 5.1 DESCRIPTION

- 1) Emerade 500 micrograms solution for injection in pre-filled pen. Emerade 500 micrograms delivers a single dose of 0.5 ml containing 500 micrograms of adrenaline (as tartrate).
- 2) Emerade 300 micrograms solution for injection in pre-filled pen. Emerade 300 micrograms delivers a single dose of 0.3 ml containing 300 micrograms of adrenaline (as tartrate).
- 3) EpiPen® Adrenaline (Epinephrine) Auto Injector 0.3 mg.

### 5.2 DOSAGE AND ROUTE OF ADMINISTRATION

0.3-0.5ml intramuscular injection, to be administered according to the SmPC provided.

### 5.3 DOSE MODIFICATION

No dose modification proposed.

### 5.4 PREPARATION AND ADMINISTRATION OF STUDY DRUG

[figure not shown]
This is a Phase IV study. AAIs will be stored in a locked cupboard on our research unit, and in accordance with SmPC recommendations (room temperature, out of direct sunlight etc). AAI will be administered according to the respective SmPC, following which devices will be disposed of in accordance with local requirements for medical waste.

### 5.5 DISPENSING AND PRODUCT ACCOUNTABILITY

All AAIs will be prescribed on local drug charts prior to study interventions, and released according to local procedure, using existing hospital pharmacy systems and logging (rather than CTIMP-specific documentation). The application for a clinical trials authority will include an exemption for study specific labelling.

**6. STUDY VISITS, PROCEDURES SCHEDULE and PATIENT FLOW DIAGRAM**

The study is summarised in Figure 2:

**Figure 2:** Study Flowchart

Following eligibility assessment (which can be done via telephone or in clinic), participants will be randomised to attend for either:

- 2 x self-administered doses of 300mcg adrenaline (given 4 hours apart), or
- 1 x self-administered dose of 500mcg adrenaline (given using an Emerade 500 device).

These study visits will happen one month apart. On the day when 2 doses of 300mcg adrenaline are administered, the order of devices used (Epipen 0.3mg, Emerade 300mcg) will also be randomised. The randomisation will follow a balanced, randomized-block crossover design, as follows:

| Study visit 1 |                | Study visit 2  |                |                |
|---------------|----------------|----------------|----------------|----------------|
|               | Morning        | Afternoon      | Morning        |                |
| 1             | Emerade 300mcg | Epipen 0.3mg   | Emerade 500mcg | -              |
| 2             | Epipen 0.3mg   | Emerade 300mcg | -              | Emerade 500mcg |
| 3             | Emerade 500mcg | -              | Emerade 300mcg | Epipen 0.3mg   |
| 4             | -              | Emerade 500mcg | Epipen 0.3mg   | Emerade 300mcg |

**Figure 3:** Randomisation table

This randomisation process is designed to reduce the influence of circadian variations on endogenous adrenaline levels and assess any impact of the order of administration of the 300mcg devices. The randomisation list will be generated using an online randomisation tool (<http://www.randomization.com>).

To reduce participant inconvenience, where eligibility has been confirmed, randomisation may occur prior to consent in order to arrange study visits to suit the participant and their family. In such an event, consent will be obtained prior to any intervention at the first study visit.

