### 6.2.2 MEDICAL ASSESSMENT

- 1) Consent and medical eligibility will be confirmed.
- 2) Physical examination and vital signs (HR, BP, Temperature, Respiratory rate and oxygen saturations) with specific assessment for evidence cardiovascular abnormalities.
- 3) Height/weight will be measured according to local protocol.
- 4) Peak expiratory flow rate will be measured using a Wright Peak Flow meter, according to local protocol.
- 5) Urine pregnancy test in female participants of child-bearing potential.

- 6) On the first visit, the surface skin-to-muscle depth (STMD) will be measured by a blinded individual on both legs, at the mid-point of the antero-lateral thigh, by ultrasound. The measurement will be withheld from both the participant/family and the study team until the end of the study for the participant.
- 7) Venous cannulation will be performed to secure venous access, from which blood samples can be taken during the study day without requiring a further needle-stick procedure. Local anaesthetic cream will be applied first for 30mins, to minimise discomfort due to cannulation. The first blood sample will be taken at least 30mins after cannulation, to limit the impact of the cannulation procedure on baseline catecholamine levels.

---

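### Allocation may be drawn and used for booking before consent and the visit 1 eligibility checks, so losses at visit 1 can unbalance the visit order that the unadjusted paired analysis relies on

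*Combined protocol and SAP*

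**What the plan says.** Section 3 describes the trial as "Open label, randomised cross-over study at a single centre", with "Two clinical visits (full day) one month apart". Section 6 sets out four sequences and says "The randomisation will follow a balanced, randomized-block crossover design"; with 12 participants that means three per sequence and six in each visit order.

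On timing, section 6 says "Following eligibility assessment (which can be done via telephone or in clinic), participants will be randomised". It then allows that "randomisation may occur prior to consent in order to arrange study visits to suit the participant and their family", and adds: "In such an event, consent will be obtained prior to any intervention at the first study visit". At visit 1, section 6.2.2 lists "Consent and medical eligibility will be confirmed", followed by physical examination, vital signs and a urine pregnancy test where relevant.

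Section 6 names an online tool for generating the list but does not say who holds it. On losses, section 4.3 says "Withdrawn participants will be replaced, where feasible", without saying whether the replacement takes the same sequence. Nothing covers a slot whose holder never consents. Section 9.3 (Analyses) compares interventions by paired t-test or Wilcoxon signed-rank test on within-person differences, with no period or sequence term.

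**The concern.** If visits are booked from the sequence, the study team knows before consent whether visit 1 is the two-injection 300mcg day or the single 500mcg day. Anyone who then declines, fails to attend or is found ineligible at visit 1 has already used a place in the block. If the list simply moves on, the treated group need not split 6:6 by visit order, and losses that depend on the known order would tilt the split one way.

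This matters because balance is the only planned protection against a difference between visits. Without a period term, a visit effect cancels from the 500 versus 300mcg mean difference only when the two visit orders are equally filled.

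**Working it through.** **The plan's own figure.** Section 9.1 gives 80% power for N = 12, a difference of 0.35 pg/ml and an SD of the difference of 0.39 pg/ml, two-sided 5%. With SE = 0.39/√12 and a noncentral t on 10 df, power is 79.97%. The figure reproduces, and this point does not alter it.

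**Sequences (section 6, Figure 3).**

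| Seq. | Visit 1 | Visit 2 | Half-day of Emerade 300 / 500 |
|---|---|---|---|
| 1 | Emerade 300, then EpiPen | Emerade 500 (morning) | morning / morning |
| 2 | EpiPen, then Emerade 300 | Emerade 500 (afternoon) | afternoon / afternoon |
| 3 | Emerade 500 (morning) | Emerade 300, then EpiPen | morning / morning |
| 4 | Emerade 500 (afternoon) | EpiPen, then Emerade 300 | afternoon / afternoon |

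Emerade 300 and 500 share a half-day in every sequence. Time of day therefore cancels within each person for the dose contrast, however the sequences are filled. Visit order does not.

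**Bias from an unequal split.** Let π be the visit effect (visit 2 minus visit 1) and δ the true 500 minus 300mcg difference. A 300-first participant contributes δ + π and a 500-first participant δ − π. With n1 and n2 in the two orders, the unadjusted mean is δ + π(n1 − n2)/12.

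- 6:6 gives 0
- 7:5 gives 2/12 = 17% of π
- 8:4 gives 4/12 = 33% of π
- 9:3 gives 6/12 = 50% of π

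**How often balance is lost.** Assumptions, none of them in the documents: permuted blocks of four, a lost slot is not reused, the list continues until 12 are treated, and losses occur at the stated rates by visit order. Each row is 40,000 simulated trials.

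| Loss, 300-first / 500-first | 6:6 kept | 8:4 or worse | Mean tilt (participants) | Expected bias (size, share of π) |
|---|---|---|---|---|
| 0 / 0 | 100% | 0% | 0 | 0 |
| 10% / 10% | 62% | 3% | 0 | 0 |
| 20% / 10% | 49% | 8% | 0.36 | 2 × 0.36/12 = 6% |
| 30% / 10% | 34% | 20% | 0.78 | 2 × 0.78/12 = 13% |

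**Effect on the test.** Simulated type I error of the unadjusted paired t-test, for π of 0.25, 0.5 and 1.0 SD of the difference:

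- 6:6: 4.4%, 2.9%, 0.6%
- 8:4: 5.2%, 5.6%, 5.1%
- 9:3: 6.1%, 9.1%, 15.1%

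Clear inflation needs about 9:3 together with a real visit effect. In the 30% / 10% scenario, 9:3 or worse occurs in about 2.5% of trials.

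**Cost of a period term.** It removes the visit bias at any split. Its variance relative to 6:6 is 3(1/n1 + 1/n2): 1.03 at 7:5, 1.13 at 8:4 and 1.33 at 9:3.

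**The case against.** The strongest reply is that this is an exploratory within-person trial in which everyone is meant to receive all three injections and the assays are analysed blind. Nobody is confounded between treatments, early randomisation is optional, and a reason to refuse because of order is speculative. The expected bias is a small share of an effect that nobody has sized, and a period term alone would remove it. This largely stands and limits the severity. It does not supply the missing rule for unused slots, and blinded assays protect measurement, not balance.

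Two practical replies also have some force. Section 4.3 counts ineligibility overlooked at screening as a withdrawal reason, so an exclusion at visit 1 may be eligible for replacement, though still not by sequence. Scheduling is also a real motive, since a single-injection day needs only one half-day for the injection and its three hours of observation. But section 3 already describes both visits as full days.

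A reader might infer more than the documents support:

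- **Families know the allocation.** No section says that they are told. It is plausible when visits are booked from the sequence, but it is an inference.
- **Imbalance lets time of day into the dose comparison.** It does not, as the sequence table shows.
- **Balance would remove an effect of the first-ever study injection.** Emerade 500 is the first injection in 6 of 12 participants and Emerade 300 in 3 of 12, so (6 − 3)/12 = 25% of such an effect enters the dose contrast even at perfect balance. Neither same-sequence replacement nor a period term changes that.
- **The device comparison is tilted too.** Device order is sequences 1 and 3 against 2 and 4. Losses that depend on the visit 1 dose give a mean device-order tilt of zero in these simulations, so no directional device bias is shown.

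**Conclusion.** The point holds as a modest design weakness that should be corrected. The protocol permits allocation to be drawn and used before consent and before the visit 1 eligibility checks, does not say what happens to unused slots, and analyses the dose contrast without a period term. The result is a bias of (n1 − n2)/12 of any visit effect. Under the assumed selective losses this averages about 6% to 13% of that effect; an individual trial that ends at 8:4 would carry 33%. Non-selective losses cause imbalance by chance but no expected bias. These sizes rest on assumed loss rates and block size, and the visit effect itself is unknown, so no bias in pg/ml can be given. The documents do not support a claim that the primary comparison is invalid.

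**What to change.** **Section 6.** Replace the pre-consent provision with wording such as: *Two full-day visits will be booked without reference to the allocation. The sequence and injection side will be revealed at visit 1, only after written consent and confirmation of eligibility, from a list kept by someone not involved in recruitment.*

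**Section 4.3.** Add: *A participant who does not complete both visits will be replaced by one allocated to the same sequence.* This also covers withdrawals after consent, which earlier consent alone would not.

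**Section 9.3, as a complement.** Add a period term to the dose comparison, so that any remaining imbalance does not bias it. In its simplest form this is a two-sample t-test between the two visit orders on the visit 1 minus visit 2 differences, with the estimate halved.

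**Cost.** A short amendment, with no change to the sample size or the procedures. Participants in sequence 4 (about 3 of 12) may wait through the morning of visit 1. Devices must be prescribed and released on the day, and someone outside recruitment has to hold the list.

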## 6.1 STUDY PROCEDURES

|   | Visit 1 | Visit 2 | Follow-up one month later   |
|---|---------|---------|---|
| Written Informed Consent (parent/ guardian)
Written Assent (young person)  | X
X  |         |   |
| Confirm eligibility   | X       |         |   |
| Medical assessment including: 

Physical examination

Height/weight

Assessment of vital signs

Peak expiratory flow

 | X       | X       |   |
| Urine pregnancy test in female participants of child-bearing potential  | X       | X       |   |
| Ultrasound assessment of surface-muscle depth (blinded)   | X       |         |   |
| HRQL assessments
(in both young person and parent/guardian): 

FAQLQ

FAIM

Self-efficacy

                                | X       | X       | X
Questionnaires done at home and then returned to research team by post or email scan |
| Venous cannulation (with prior use of local anaesthetic cream to minimise discomfort)   | X       | X       |   |
| Non-invasive cardiac monitoring   | X       | X       |   |
| Education of AAI technique, followed by self-administration of AAI and collection of blood samples thereafter.  | X       | X       |   |
| Follow-up telephone call next day   | X       | X       |   |

## 6.2 PRE-INTERVENTION ASSESSMENTS AND PROCEDURES

### 6.2.1 PRE-STUDY PRECAUTIONS

Participants will be asked to avoid tea/coffee/cocoa/cola in the 24 hours prior to a study visit, in order to minimise intake of caffeine or methyloxanthines which may affect plasma catecholamine levels.

### 6.2.2 MEDICAL ASSESSMENT

- 1) Consent and medical eligibility will be confirmed.
- 2) Physical examination and vital signs (HR, BP, Temperature, Respiratory rate and oxygen saturations) with specific assessment for evidence cardiovascular abnormalities.
- 3) Height/weight will be measured according to local protocol.
- 4) Peak expiratory flow rate will be measured using a Wright Peak Flow meter, according to local protocol.
- 5) Urine pregnancy test in female participants of child-bearing potential.

- 6) On the first visit, the surface skin-to-muscle depth (STMD) will be measured by a blinded individual on both legs, at the mid-point of the antero-lateral thigh, by ultrasound. The measurement will be withheld from both the participant/family and the study team until the end of the study for the participant.
- 7) Venous cannulation will be performed to secure venous access, from which blood samples can be taken during the study day without requiring a further needle-stick procedure. Local anaesthetic cream will be applied first for 30mins, to minimise discomfort due to cannulation. The first blood sample will be taken at least 30mins after cannulation, to limit the impact of the cannulation procedure on baseline catecholamine levels.

---

### 6.2.2 HRQL ASSESSMENTS

The impact of AAI self-administration (in a non-reaction, supervised setting) on HRQL measures will be assessed both from the participant's and their parent/guardian's perspective using:

- 1) abbreviated versions of disease-specific validated "food-allergy quality of life questionnaire" (FAQL-Q) in its parental, and teenage forms;
- 2) Food allergy independent measure (FAIM)
- 3) Food allergy self-efficacy questionnaire

These will be completed prior to the first intervention on the first study day, approximately 1 month later (which should coincide with the second study visit), and one month later.

---

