### 2.3 STUDY HYPOTHESES

- 1) In young people over 40kg, intramuscular self-injection of 500mcg adrenaline results in a greater peak plasma adrenaline level compared to 300mcg injection, without causing a significant increase in adverse events.
- 2) In young people over 40kg, self-injection using an AAI with a 23mm needle will result in a more-favourable PK profile than an alternative device with a 15mm needle, without causing a significant increase in adverse events.
- 3) Self-administration of AAI as a method to provide training in the use of AAI is associated with a positive impact of HRQL measures in food-allergic teenagers.

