#### 9.2.1 ANALYSIS SET

Children aged 13-18 years (inclusive) self-administering AAI according to the study protocol. Analysis will be as treated.

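### No HRQL follow-up is planned for teenagers who stop between the first injection and visit 2, and the single analysis set can exclude failed attempts, so the test of hypothesis 3 is open to selection

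*Combined protocol and SAP*

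**What the plan says.** Hypothesis 3 (section 2.3), stated for teenagers with food allergy, reads: "Self-administration of AAI as a method to provide training in the use of AAI is associated with a positive impact of HRQL measures". Section 9.3, planned analysis 4, tests it as change from baseline one month after each study visit. No group goes without injection.

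**Timing.** Section 6.2.2 (HRQL Assessments) has the questionnaires completed by teenager and parent before the first injection, then "approximately 1 month later (which should coincide with the second study visit), and one month later". The section 6.1 table marks the second set under visit 2. Only the last set, one month after visit 2, is remote: "Questionnaires done at home and then returned to research team by post or email scan".

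**Withdrawal.** Section 4.3 introduces its list with "In addition the participant may be withdrawn for any of the following reasons". One entry is a significant protocol deviation that irreversibly affects data integrity, with the example "failure to administer adrenaline autoinjector correctly". The only contact it describes after withdrawal is follow-up of an adverse event. It adds: "Withdrawn participants will be replaced, where feasible".

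**Analysis.** Section 9.2.1 defines one set: "Children aged 13-18 years (inclusive) self-administering AAI according to the study protocol", analysed as treated. Section 9.2.2 records reasons for missing data and rules out imputation. Sections 4.3 and 10.3 keep what was already collected from withdrawn participants; section 4.3 makes an exception if the family asks for destruction.

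**The concern.** Excluding an incorrect injection is sensible for Cmax, Tmax and AUC, because the dose was not delivered as intended. For self-efficacy and quality of life the position differs: failing the injection, or being upset by it, is part of what the training experience does to a teenager. Section 1.1 gives fear of self-administration and of side-effects among the reasons teenagers do not use their device, so these are the people the intervention is meant to help.

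If they leave after visit 1, the plan holds their baseline and nothing later. If they stay after an incorrect injection, section 9.2.1 read literally leaves them out. With no comparison group, nothing offsets a loss of this kind. The result for hypothesis 3 could then describe mainly those who injected correctly and came back. The parents' questionnaires follow the same schedule and have the same gap.

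**Working it through.** **Plan's own figure.** The only power figure is in section 9.1: 80% for a difference of 0.35 pg/ml with 12 participants and an SD of the difference of 0.39. A noncentral t calculation with 10 degrees of freedom gives 0.800, so it reproduces. It concerns plasma adrenaline and says nothing about HRQL.

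**Following each type of participant through the plan**

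| Participant | HRQL scores the schedule provides | Change from baseline | Place in the 9.2.1 set |
|---|---|---|---|
| Completes both visits, injections correct | Baseline, visit 2, home | Both time points | Included |
| Attempts an injection at visit 1, stops before visit 2 | Baseline only | Cannot be computed | Out if the injection was incorrect; otherwise in, but with no follow-up score |
| Injects incorrectly at visit 1, is not withdrawn, returns | All three | Both time points | Out on a literal reading; the as-treated sentence leaves it unclear |
| Withdrawn at visit 2 | Baseline and visit 2 | First time point | Depends on the reason |

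The problem lies in rows two and three. Keeping data already collected does not help row two, because the only HRQL data collected are the baseline scores. For row three the score exists, but section 9.2.1 does not say whether it counts, and it is not reconciled with the inclusion of withdrawn participants' data in sections 4.3 and 10.3.

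**Illustration on assumed values.** Let w participants attempt an injection, stop before visit 2 and all be replaced, leaving 12 completers. Let g be the completers' mean change minus the leavers', in SDs of the change score, with improvement positive. If the completers' mean is m, then

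mean in all who attempted = (12m + w(m − g)) / (12 + w) = m − g × w/(12 + w),

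so the completers' mean overstates the change by g × w/(12 + w).

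| w | w/(12 + w) | g = 0.5 | g = 1.0 | g = 1.5 |
|---|---|---|---|---|
| 1 | 1/13 = 0.077 | 0.04 | 0.08 | 0.12 |
| 2 | 2/14 = 0.143 | 0.07 | 0.14 | 0.21 |
| 3 | 3/15 = 0.200 | 0.10 | 0.20 | 0.30 |
| 4 | 4/16 = 0.250 | 0.13 | 0.25 | 0.38 |

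With g = 0 the bias is zero; with g negative the change is understated by the same amounts.

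**Role of replacement.** Replacement restores the number, not the mix. Without it the overstatement is g × w/12; for w = 2 and g = 1 that is 2/12 = 0.17 SD, against 0.14 SD with it. The selection therefore comes from the missing follow-up and the analysis set, and replacement only makes the loss less visible. Without replacement n falls to 11, 10, 9 or 8, and the paired change detectable with 80% power (two-sided 5%) rises from 0.89 SD at n = 12 to 0.94, 1.00, 1.07 or 1.16 SD.

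**The case against.** The case against has several parts.

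- Section 6.2.2 sets the assessment by time and only expects it to coincide with visit 2. Nothing forbids posting the questionnaire earlier.
- Withdrawal for an incorrect injection is discretionary and tied to irreversible harm to data integrity. Section 6.2.3.2 requires trainer-pen practice and clinician supervision, so failures may be rare.
- Someone withdrawn at visit 2 already has one post-injection score.
- Hypothesis 3 concerns self-administration, so a teenager who did not manage it could legitimately fall outside the target.
- The direction is not established. Two full-day visits are reason enough to leave, and the related study in section 1.1 found better HRQL after self-injection whatever the reaction severity.
- HRQL is a secondary outcome in a study that section 9.1 calls exploratory, and the lack of a control limits hypothesis 3 more than one or two leavers would.
- The most distressed families may be the least likely to reply.

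Most of this stands and sets the limits of the point. A reader might infer that every failed injection leads to withdrawal and loss of data, or that the HRQL result must be inflated by some stated amount. The documents support neither: withdrawal is optional, replacement is where feasible, and no HRQL variance or dropout rate is given.

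Three things do not fall away. An option that is merely not forbidden is not a plan, and following the section 6.1 table as written yields no follow-up score. Restricting hypothesis 3 to correct injections is a possible choice, but section 9.2.1 does not present it as one; it applies one set to all outcomes. And the study cited in section 1.1 concerned self-injection as treatment during a reaction; nothing cited describes teenagers whose attempt failed.

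**Conclusion.** The point holds as a gap in follow-up and in the definition of the analysis set. The HRQL and self-efficacy analysis is open to selection on correct injection and return, and section 9.2.1 is not reconciled with the rule that withdrawn participants' data are included. A bias towards hypothesis 3 is plausible, on the assumption that those who failed or were distressed do worse than completers. The documents do not test that assumption, so neither size nor direction can be determined.

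On the assumed range of one to four leavers and a gap of 0.5 to 1.5 SD, the overstatement would be 0.04 to 0.38 SD. If nobody stops between the first injection and visit 2, and every injection is correct, there is none. The pharmacokinetic conclusions are unaffected. This is a worthwhile, inexpensive improvement to a secondary outcome, not a flaw that threatens the trial.

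**What to change.** 1. In sections 4.3 and 6.2.2 (HRQL Assessments), state that any participant who attempts at least one self-injection and then stops is sent the 1-month questionnaires by the post or email route already used after visit 2, and that the parent or guardian is sent theirs, unless they decline contact. The withdrawal rules themselves need no change.
2. In section 9.2.1, keep the per-protocol set for the pharmacokinetic outcomes and define a separate HRQL and self-efficacy set of everyone who attempted the first self-injection, correct or not. Keep participants who were later replaced in that set, and say how it fits with the rule on withdrawn participants' data.
3. Report how many in that set have no follow-up questionnaire, alongside the reasons that section 9.2.2 already requires.

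The cost is protocol wording and one questionnaire pack per family that stops early. Visits, blood sampling, sample size and the pharmacokinetic analysis stay as they are. Some withdrawn families will not reply, so the change reduces the selection and makes it visible without removing it. It also does nothing about the missing control group.
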